The first dose of talimogene laherparepvec will be up to 8.0 mL of 10^6 PFU/mL. The second injection, up to 8.0 mL of 10^8 PFU/mL, will be administered 3 weeks (+3 days) after the initial injection (ie, no sooner than day 22 but should not be delayed more than 3 days after the 3 week time point). All subsequent injections, up to 8.0 mL of 10^8 PFU/mL, will be administered every 3 weeks (\pm 3 days). The maximum volume of talimogene laherparepvec administered at any dose is 4.0 mL for any individual tumor lesion. The maximum volume in any treatment visit is 8.0 mL. When talimogene laherparepvec and pembrolizumab are administered on the same day, it is recommended that talimogene laherparepvec be administered first. Refer to [Section 6.2.1](#).

Phase 3:

The initial dose of double-blind treatment is up to 8.0 mL of 10^6 PFU/mL talimogene laherparepvec/placebo (talimogene laherparepvec formulation excipients as described in the Talimogene Laherparepvec [Investigator's Brochure](#)). The second dose up to 8.0 mL of 10^8 PFU/mL talimogene laherparepvec/placebo should be administered 21 (+ 3) days after the initial dose. Subsequent doses up to 8.0 mL of 10^8 PFU/mL talimogene laherparepvec/placebo should be given every 3 weeks (\pm 3 days). The maximum volume of talimogene laherparepvec/placebo administered at any dose is 4.0 mL for any individual tumor lesion. The maximum volume at any treatment visit is 8.0 mL. When talimogene laherparepvec/placebo and pembrolizumab are administered on the same day, it is recommended that talimogene laherparepvec/placebo be administered first.

Non-Amgen Investigational Product Dosage and Administration: Pembrolizumab will be manufactured by Merck. Pembrolizumab is supplied in 100 mg/4mL vials (25 mg/mL) solution for intravenous infusion.

Phase 1b/3:

Pembrolizumab at a dose of 200 mg will be administered intravenously every 3 weeks (\pm 3 days). See [Section 6.2.2.2](#) for additional information regarding dosage and administration of pembrolizumab.

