The maximum volume of talimogene laherparepvec/placebo administered at any dose is 4.0 mL for any individual tumor lesion. The maximum volume at any treatment visit is 8.0 mL. Investigators are encouraged to use the maximum volume whenever lesions allow. The recommended volume of talimogene laherparepvec/placebo to be injected into the tumor(s) is dependent on the size of the tumor(s) and should be determined according to the injection volume guideline in [Table 2](#).

Table 2. Talimogene Laherparepvec Injection Volume Guideline Based on Tumor Size

Tumor Size (longest dimension)	Maximum Injection Volume
> 5.0 cm (50 mm)	4.0 mL
> 2.5 cm (25 mm) to 5.0 cm (50 mm)	2.0 mL
> 1.5 cm (15 mm) to 2.5 cm (25 mm)	1.0 mL
> 0.5 cm (5 mm) to 1.5 cm (15 mm)	0.5 mL
\leq 0.5 cm (5 mm)	0.1 mL

On each treatment day, prioritization of injections is recommended as follows:

- any new injectable tumor that has appeared since the last injection
- by tumor size, beginning with the largest tumor
- any previously uninjectable tumor(s) that is now injectable

It is recommended that each lesion should receive the maximum amount possible to inject due to tumor properties at each visit before moving on the next lesion, using the prioritization model above and the injection volume guideline based on tumor size per [Table 2](#). Tumor measurements for injection volume determination may be done by caliper measurements and/or by ultrasound guided measurements. Most recent prior radiographic tumor assessment measurements may be used to determine injection volume if caliper measurements and/or ultrasound guided measurements are not feasible and/or unavailable. The lesions injected will be recorded on the CRF.

Note: Continued injection into nodal lesions that have decreased to < 10 mm is up to the discretion of the investigator.

Subjects will be treated with talimogene laherparepvec/placebo until subjects have achieved a iCR, no injectable lesions, confirmed iPD (response per irRECIST), intolerance of study treatment, 24 months from the date of the first dose of talimogene laherparepvec/placebo, or end of study, whichever occurs first. Due to the mechanism of action, subjects may experience growth in existing tumors or the appearance of new tumors prior to maximal clinical benefit of study therapy. The dose, start date, and lot number of talimogene laherparepvec/placebo are to be recorded on each subject's CRF.

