10.1.3 Covariates and Subgroups

To explore the robustness of efficacy signal in phase 1b, iORR may also be estimated separately by PD-L1 status (positive/not positive) or other covariates listed below.

Besides the stratification factors for randomization in phase 3 of HPV status at baseline (HPV- negative vs HPV-positive) and ECOG performance status (0 vs 1), the following covariates will be used to examine efficacy and safety in subgroups or in multivariate analyses as appropriate:

- Region (South America vs North America vs. EU vs. Asia vs Other or phase 1b; South America vs North America vs EU vs Japan vs Other Asia vs Other for phase 3)
- Age at baseline: < 50, ≥ 50; < 65, ≥ 65; < 75, ≥ 75 years
- Sex (female vs male)
- Prior smoking (never vs former vs current)
- HSV-1 serostatus (positive vs negative)
- **HPV status (positive vs negative vs unknown) (phase 1b)**
- The sum of diameters of target lesions
- Weight loss >5% in the previous 6 months
- Primary tumor site(oral cavity vs oropharynx vs hypopharynx vs. larynx)
- Brain metastasis status (baseline brain metastasis vs no baseline brain metastasis)
- Prior radiotherapy for the treatment of SCCHN
- Extent of disease (metastatic vs locoregionally recurrent only)
- Prior lines of therapy in recurrent/metastatic setting (0, 1 or 2)
- PD-L1 status at baseline (PD-L1 positive vs PD-L1 not positive)
- Baseline CD8 + T cell density
- Maximum blinded investigational product total volume per treatment administration ≥ 4 mL at highest concentration (yes, no)

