4.2 Planned Covariates

To explore the robustness of efficacy signal in phase 1b, iORR may also be estimated separately by PD-L1 status (positive/not positive) or other covariates listed below.

- Region (South America vs North America vs EU vs Asia vs Other for phase 1b)
- Age at baseline: < 50 , ≥ 50 ; < 65 , ≥ 65 ; < 75 , ≥ 75 years
- Sex (female vs male)
- Prior smoking (never vs former vs current)
- HSV-1 serostatus (positive vs negative)

- HPV status (positive vs negative vs unknown) (phase 1b)
- The sum of diameters of target lesions
- Weight loss >5% in the previous 6 months
- Primary tumor site (oral cavity vs oropharynx vs hypopharynx vs larynx)
- Brain metastasis status (baseline brain metastasis vs no baseline brain metastasis)
- Prior radiotherapy for the treatment of SCCHN
- Extent of disease (metastatic vs locoregionally recurrent)
- Prior lines of therapy in recurrent/metastatic setting (0, 1 or 2)
- PD-L1 status at baseline (PD-L1 positive vs PD-L1 not positive)
- CD8+ T cell density
- Maximum blinded investigational product total volume per treatment administration > 4 mL at highest concentration (yes, no)

Other covariates reported in the literature or from other Amgen studies maybe considered as appropriate at the time of analysis.

5. Hypotheses and/or Estimations

Phase 1b:

Talimogene laherparepvec in combination with pembrolizumab will be safe and well tolerated in subjects with recurrent or metastatic SCCHN.

6. Definitions

1-year, 2-year, and 3-year survival

The Kaplan-Meier (KM) estimate of the overall survival (OS) at 1 year, 2 years, and 3 years.

Actual Follow-Up Time

Actual follow-up time for a subject is calculated from the enrollment (phase 1b) date to the last on-study date (ie, death date, or date last known to be alive for subjects still alive).

Baseline

Baseline in general refers to study day 1. The baseline value of a parameter (eg, vital signs, laboratory tests, and tumor measurement) is considered to be the latest value prior to receiving any study drug (ie, on or prior to the first date of dosing) in the respective phase of the study. Parameters that are obtained on the same day as the first date of dosing are assuming to be pre-dose. For subjects who are not dosed, the

baseline value of a parameter is considered to be the latest value prior to the enrollment date.

Best overall response (iBOR) per irRECIST

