10.4 Demographic and Baseline Characteristics

Summary statistics of the following demographic and baseline characteristics will be tabulated using the SAS for phase 1b of the study.

- Region (South America vs North America vs EU vs Asia vs Other for phase 1b; South America vs North America vs EU vs Japan vs Other Asia vs Other for phase 3)
- Age at baseline: < 50, ≥ 50; < 65, ≥ 65; < 75, ≥ 75 years
- Sex (female vs. male)
- Prior smoking (never vs former vs current)
- HSV-1 serostatus (positive vs negative)
- The sum of diameters of target lesions
- Weight loss > 5% in the previous 6 months

- Primary tumor site (oral cavity vs oropharynx vs hypopharynx vs. larynx)
- Brain metastasis status (baseline brain metastasis vs no baseline brain metastasis)
- Prior radiotherapy for treatment of SCCHN
- Extent of disease (metastatic vs locoregionally recurrent)
- Prior lines of therapy in recurrent/metastatic setting (0, 1 or 2)
- PD-L1 status at baseline (positive versus not positive)
- CD8+ T cell density
- HPV (HPV- negative vs HPV-positive vs unknown)
- ECOG performance status (0 vs 1)
- Maximum blinded investigational product total volume per treatment administration > 4 mL at highest concentration (yes, no)

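### Maximum injected volume at the highest concentration is a post-baseline variable, but the SAP lists it as an efficacy covariate and a baseline characteristic; separately, its cut-off differs between protocol and SAP

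*SAP*

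**What the plan says.** SAP 4.2 opens by saying that "iORR may also be estimated separately by PD-L1 status (positive/not positive) or other covariates listed below". The list that follows ends with "Maximum blinded investigational product total volume per treatment administration > 4 mL at highest concentration", coded yes or no. SAP 10.4 states that "Summary statistics of the following demographic and baseline characteristics will be tabulated using the SAS for phase 1b of the study" and includes the same line, again with > 4 mL. Tabulation there is planned, not optional.

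Protocol 10.1.3 has the corresponding entry with a different symbol: "Maximum blinded investigational product total volume per treatment administration ≥ 4 mL at highest concentration (yes, no".

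Three other provisions bear on the variable:

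- **Baseline.** SAP Section 6 defines it: the value of a parameter "is considered to be the latest value prior to receiving any study drug".
- **Schedule.** The first talimogene dose is at 10^6 PFU/mL. The protocol synopsis and 7.2.3 then say: "The second injection, up to 8.0 mL of 10^8 PFU/mL, will be administered 3 weeks (+3 days) after the initial injection". Later doses follow every 3 weeks, for up to 24 months.
- **Volume.** Protocol 6.2.1.1 sets volume by lesion size (Table 2) and states: "The maximum volume of talimogene laherparepvec/placebo administered at any dose is 4.0 mL for any individual tumor lesion". The cap per visit is 8.0 mL. Protocol 6.2.1.2 allows volume to fall because of a disease response.

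**The concern.** A subgroup formed from what happened after treatment began is not a subgroup of the subjects as enrolled. Here the classifier is a maximum over doses, so it can only move from *no* to *yes* as doses accumulate. How many doses a subject gets depends on progression, because confirmed iPD ends dosing. A difference in iORR between the two groups could then reflect time on treatment, or lesion size and shrinkage, with no effect of volume. A reader who finds the variable in a baseline table would have no warning of this.

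The cut-off raises a different question, that of reproducibility. Two analysts, one working from the protocol and one from the SAP, could put the same subject in opposite groups.

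**Working it through.** The documents give no sample size, power or rate for this subgroup, so there is no stated figure to reproduce.

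**1. Is it a baseline variable?** Baseline is pre-dose (SAP Section 6). The highest concentration is first given in week 3. The variable has no value at baseline for any subject, so its listing in SAP 10.4 conflicts with the SAP's own definition.

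**2. Who is *no* by construction?** The EAS is a subset of the SAS (SAP 7.2), which requires one dose of either product (SAP 7.4). The FAS requires one dose of each (SAP 7.3). Neither requires a 10^8 dose. Subjects without one are counted and can only be *no*.

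**3. How large could the bias be if volume has no effect on response?** Let *p* be the true iORR, and *a* and *b* the chances that a responder and a non-responder are classed *yes*. Then

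- iORR(yes) = p·a / [p·a + (1 − p)·b]
- iORR(no) = p·(1 − a) / [p·(1 − a) + (1 − p)·(1 − b)]

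The two are equal only when a = b. From the documents, p = 11% (SAP 10.5.2.1) and the EAS is about 27 subjects (protocol 10.2.1), so about 3 responders (3/27 = 11.1%). Everything else below is assumed.

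*A. Crossing is independent at each 10^8 dose, with chance q.* Non-responders receive 0, 1, 2 or 3 such doses with probabilities 0.15, 0.15, 0.35, 0.35; responders receive 9. At q = 0.2:

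- b = 0.15(0.2) + 0.35(0.36) + 0.35(0.488) = 0.327
- a = 1 − 0.8^9 = 0.866
- Overall *yes* = 0.11(0.866) + 0.89(0.327) = 0.386
- iORR(yes) = 0.0952/0.386 = 24.7%; iORR(no) = 0.0148/0.614 = 2.4%

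*B. Volume is constant within a subject.* 30% would be *yes*, all responders receive a 10^8 dose, and a share e of non-responders never does. Then a = 0.3 and b = 0.3(1 − e). At e = 0.2, iORR(yes) = 0.033/0.2466 = 13.4% and iORR(no) = 0.077/0.7534 = 10.2%.

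*C. Responders' lesions shrink.* They can cross only in their first two 10^8 doses; non-responders are as in A with q = 0.2. Then a = 1 − 0.8² = 0.36 and b = 0.327, giving 0.0396/0.3305 = 12.0% against 0.0704/0.6695 = 10.5%.

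*D. As C, but responders cross with chance 0.1 per dose.* Then a = 1 − 0.9² = 0.19, giving 0.0209/0.3118 = 6.7% against 0.0891/0.6882 = 12.9%.

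| Scenario (true iORR 11%) | iORR, *yes* | iORR, *no* |
|---|---|---|
| A, q = 0.1 | 30.0% | 5.5% |
| A, q = 0.2 | 24.7% | 2.4% |
| A, q = 0.3 | 20.7% | 0.9% |
| B, e = 0 | 11.0% | 11.0% |
| B, e = 0.1 | 12.1% | 10.6% |
| B, e = 0.2 | 13.4% | 10.2% |
| C | 12.0% | 10.5% |
| D | 6.7% | 12.9% |

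A is an extreme case. Protocol 3.5.1 estimates a median treatment period of 7 months. If half of subjects are treated that long and all responders (11%) are among them, at least (50 − 11)/89 = 44% of non-responders are too. That fits poorly with three 10^8 doses at most, although the 7 months covers study treatment as a whole.

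**4. Does grouping at the second dose remove the time-on-treatment component?** Among subjects who received that dose, each has had one chance to cross. If the chance q is the same for responders and non-responders, a = b = q and iORR(yes) = p·q/q = p, and likewise for *no*. Any link between lesion size and prognosis remains.

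**5. Where do the two cut-offs differ?** Counting combinations of the Table 2 maximum volumes, unweighted by how often they occur:

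| Lesions injected | Combinations | > 4 mL | ≥ 4 mL | Exactly 4.0 mL |
|---|---|---|---|---|
| 1 | 5 | 0 | 1 | 4.0 |
| 2 | 15 | 5 | 6 | 2.0 + 2.0 |
| 3 | 35 | 19 | 20 | 2.0 + 1.0 + 1.0 |

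Because of the per-lesion cap, a subject with one injectable lesion can never be *yes* under the SAP but can be under protocol 10.1.3. One injectable lesion is enough for eligibility (criterion 105).

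**The case against.** The strongest reply is that little rests on this. The subgroup iORR is something the SAP may do, all phase 1b endpoints are descriptive (SAP 10.5.2.1), and no test, model or decision rule uses the variable. SAP Section 11 records that the sponsor had already decided not to proceed to phase 3. Exposure above 4 mL is already summarised in SAP 10.6.6. All of this stands, and it sets the severity.

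It is also fair that the bias may be small or absent. With constant volume and every subject reaching the second dose it is zero, and shrinking lesions in responders or growing lesions in non-responders work against the time-on-treatment effect. That stands too: the subgroup is open to bias, and no more can be claimed.

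A reader might go further in three ways that the documents do not support:

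- *That subjects who stop before week 3 cannot respond.* Pembrolizumab may continue after talimogene stops for talimogene-related toxicity (protocol 6.2.1.2). Imaging runs until confirmed iPD or new anticancer therapy (protocol 3.1.3.2), and follow-up assessments are sought in subjects who stop without iPD (SAP 3.1.3.3).
- *That the choice of cut-off reverses the apparent effect.* The symbol changes who is classified *yes*; no change of sign follows from it.
- *That the cut-off mismatch causes the bias.* The bias comes from the post-baseline definition and would exist with either symbol.

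The mismatch is also narrow. The SAP uses > 4 mL throughout, as do the protocol's safety reviews (synopsis and 10.4.1.2). Only protocol 10.1.3 differs.

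**Conclusion.** The point holds, at minor severity, as two separate defects.

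First, a variable that cannot be observed before week 3 is listed as a baseline characteristic and as an efficacy covariate, with no landmark, fixed dosing window or time-dependent method. The optional iORR subgroup is open to bias. Its size and net direction cannot be derived from the documents: at a true 11% the assumed scenarios run from no difference, through 13% versus 10%, to 30% versus 5%, and one reverses to 7% versus 13%. With about 27 subjects and a 30% *yes* share, that group has about 8 members (0.3 × 27 = 8.1), so one responder moves its rate by about 12 points (1/8). Chance alone would make the comparison hard to read.

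Second, protocol and SAP classify subjects at exactly 4.0 mL oppositely, and SAP Section 11 does not record the change.

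Overall iORR and the DLT endpoint do not use the variable and are unaffected. The entry also refers to blinded product, which does not fit the open-label phase 1b (protocol 5.1).

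**What to change.** - Remove the variable from SAP 4.2 and 10.4 and report it only under exposure, in SAP 10.6.6.
- If iORR by volume is still wanted, group by the volume given at the second talimogene dose, among subjects who received it, and count response from then on. The first scheduled scan is at week 9, so a second dose given on schedule at week 3 loses no scheduled assessment. State that lesion size still confounds the comparison.
- Reconcile the analysis cut-off between protocol 10.1.3 and the SAP, and note any change in SAP Section 11.
- Drop the word blinded from the entry for phase 1b.

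The cost is wording, plus one optional exploratory subgroup dropped or redefined. No data collection changes. The SAP also covers the follow-up and final analyses (SAP Section 1), so the correction can still take effect there.

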4.1.3 Exploratory Endpoints

- Phase 1b
 - ORR, CRR, BOR, DCR, and DOR (response evaluation by investigator using modified RECIST v1.1)
 - Incidence of clearance of talimogene laherparepvec DNA from blood and urine
 - Rate of detection and subject incidence of talimogene laherparepvec DNA and virus from blood, urine, exterior of occlusive dressing, surface of injected lesions, and oral mucosa
 - Response rates in injected and uninjected lesions: evaluable lesion incidence of a $\geq 30\%$ decrease in lesion length for ≥ 4 weeks
 - Incidence of detection of talimogene laherparepvec DNA in lesions suspected to be herpetic in origin
 - Potential biomarkers which predict and/or are correlated with clinical outcomes to talimogene laherparepvec and pembrolizumab

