Best overall response (iBOR) of complete response (iCR), partial response (iPR), stable disease (iSD), progressive disease (iPD) or unevaluable (iUE) will be derived based on investigator assessment using immune-related RECIST [irRECIST]) (see protocol Appendix D). The visit overall response assessments occurring after initiation of non-study anticancer therapy **will not be included. The visit overall response assessments occurring on or after** a complete or partial removal/reduction of any target or non-target lesion containing cancer or with unknown pathology results will not be included **except an iPD observation.**

Confirmation of iCR, iPR, and iPD is required as noted in the individual definitions for iCR, iPR and iPD per irRECIST. For the derivation of iBOR, the overall visit response will be considered iSD if it is an unconfirmed iCR or iPR, and iUE if it is either iSD earlier than 56 days **after the date of first dose** (phase 1b) or an unconfirmed iPD when confirmation of iPD is required (eg, initial iPD without clinical deterioration). As indicated in [Table 1](#), iBOR is defined as the best overall visit response in the following order: iCR, iPR, iSD, iPD, or iUE.

Table 1. Matrix of Determining iBOR per irRECIST

Visit Overall Response Sequence	Examples	Best Overall Response	Specifications
* , iCR, iCR, *	iPR, iCR, iCR iCR, iCR, iPD	iCR	A confirmatory iCR must be at least 4 weeks (28 days) later; a subsequent iCR within 28 days will not be valid for confirmation and will be ignored; the iCR will also not be confirmed if there is a subsequent iPR/iSD/iPD at any time prior to the next iCR.
* , iPR, iPR, * * , iPR, iCR/iPR, non-iCR, * * ,iCR, iPR, *	iPR, iPR, iPD iPR, iCR, iPD iCR, iPR, iPD	iPR	Criteria for iBOR=iCR not met. A confirmatory iPR/iCR must be no less than 4 weeks (28 days) later; a subsequent iPR/iCR within 28 days will not be valid for confirmation and will be ignored; the iPR will also not be confirmed if there is a subsequent iSD/iPD at any time prior to the next iPR/iCR.
* , iSD, * * , iCR, non-iPR/iCR, * * , iPR, non-iPR/iCR, *	iCR iPD, iCR iPR iPD, iPR, iSD iSD iPD, iSD, iPD	iSD	Criteria for iBOR=iCR or iPR not met. iSD must be ≥ 56 days from first dose (phase 1b); however, this is not required for an unconfirmed iCR/iPR.

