* , iPD, iPD, * * , iPDrcd, * * , iPD, non-iPD, iPD, * iPDrcd = iPD from rapid clinical deterioration as the reason for ending radiographic follow-up.	iPD, iPD iPD, iSD, iPD, iPD iPD, iUE, iPD iPDrcd	iPD	Criteria for iBOR=iCR, iPR, or iSD not met. A consecutive confirmatory iPD must be no less than 4 weeks (28 days) later unless there is rapid clinical deterioration; iPDrcd does not require confirmation. If an initial visit overall response of iPD is not confirmed, then a subsequent iPD does not need to be confirmed for a subject overall response of iPD.
* , iSD, * iPD	iSD iUE, iSD iPD iUE, iPD	iUE	Criteria for iBOR=iCR, iPR, iSD, or iPD not met. iSD must be < 56 days from first dose (phase 1b).

Best overall response (BOR) per RECIST v1.1

Best overall response (BOR) of complete response (CR), partial response (PR), stable disease (SD), progressive disease (PD) or unevaluable (UE) will be derived based on investigator assessment using RECIST v1.1 (see protocol Appendix E). The visit overall response assessments occurring after initiation of non-study anticancer therapy **will not be included. The visit overall response assessments occurring on or after a complete or partial removal/reduction of any target or non-target lesion containing cancer or with unknown pathology results will not be included except a PD observation.**

Confirmation of CR and PR is not required. For the derivation of BOR, the overall visit response will be UE if SD is earlier than 56 days **after the date of first dose**. As indicated in protocol Table 15, BOR is defined as the best overall visit response in the following order: CR, PR, PD, SD, or UE.

BOR per modified RECIST v1.1 for Phase 1b subjects will follow the same derivation.

Disease control rate (iDCR) per irRECIST

Disease control rate (iDCR) per irRECIST is defined as the incidence of an iBOR of iCR or iPR or iSD among the set of subjects analyzed.

Disease control rate (DCR) per RECIST v1.1

Disease control rate (DCR) per RECIST v1.1 is defined as the incidence of a BOR of CR or PR or SD among the set of subjects analyzed.

Duration of response (iDOR) per irRECIST

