10.5.2 Analyses of Secondary Efficacy Endpoints

10.5.2.1 Phase 1b

The primary analysis of efficacy for the phase 1b will be based on the EAS, with secondary analysis based on the FAS overall and excluding subjects in the EAS. All endpoints of the phase 1b will be descriptively analyzed.

The main efficacy endpoint in the phase 1b for the phase 3 decision will be the iORR with or without confirmation of response. Given the observed iORR in the Efficacy Analysis Set, the Bayesian posterior probability will be calculated that the true combination iORR exceeds the expected ORR for pembrolizumab by an absolute amount (δ). The expected iORR for pembrolizumab in the study population with 9 weeks minimum potential follow-up is approximately 11% and will be represented by a $\text{beta}(2.2, 17.8)$ distribution with mean 0.11 and precision 20.0. The iORR for the combination will be represented by a $\text{beta}(0.2, 1.8)$ distribution with mean 0.11 and precision 2.0. Given the observed iORR, the posterior probability will be calculated for a δ increase from 0% to 30% in 5% increments as well as a 90% credible region for δ (see [REDACTED]).

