10.5.3 Analyses of Exploratory Endpoints

10.5.3.1 Phase 1b

The exploratory analysis for Phase 1b for ORR, CRR, BOR, DCR, and DOR (response by investigator using modified RECIST v1.1) will be analyzed using the analysis methods described in **the first paragraph of Section 10.5.2.1** above, where applicable.

- Response rates in injected and uninjected lesions:
L-ORR and the incidence of L-PR and L-CR separately at the lesion level will be summarized by enrolled/randomized treatment for subjects in the EAS (phase 1b) and FAS(G)(phase 3) for the Injected Lesion Analysis Set and the Uninjected Lesion Analysis Set separately, and also for the corresponding evaluable analysis sets. Waterfall plots for the maximum percent decrease in the lesion diameter will also be provided. The number of subjects will be provided with at least one lesion in each analysis as well as the distribution of the number of lesions per subject. The subject incidence of an L-CR or L-PR and each individually will also be summarized separately for subjects with a lesion included in the Injected Lesion and Uninjected Lesion analysis sets and corresponding evaluable analysis sets.

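### RECIST v1.1 best overall response ranks PD above SD, so phase 1b subjects with stable disease who later progress drop out of the exploratory DCR

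*SAP*

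**What the plan says.** The rule is in SAP Section 6 (Definitions), under BOR per RECIST v1.1: "BOR is defined as the best overall visit response in the following order: CR, PR, PD, SD, or UE". The SAP points to protocol Table 15 for this order. Early stable disease is handled separately: "the overall visit response will be UE if SD is earlier than 56 days" after first dose. Visits after non-study anticancer therapy are left out. Visits on or after removal of a lesion with cancer or unknown pathology are left out too, unless they show PD. For this part of the trial, "BOR per modified RECIST v1.1 for Phase 1b subjects will follow the same derivation".

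The rate built on it follows in the same section: "Disease control rate (DCR) per RECIST v1.1 is defined as the incidence of a BOR of CR or PR or SD".

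For irRECIST, Section 6 gives the opposite ranking of the two middle categories: "iBOR is defined as the best overall visit response in the following order: iCR, iPR, iSD, iPD, or iUE".

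SAP 4.1.3 lists BOR and DCR per modified RECIST v1.1 as exploratory. SAP 10.5.3.1 says they "will be analyzed using the analysis methods described in" the first paragraph of 10.5.2.1. That paragraph names the Efficacy Analysis Set (EAS), the Full Analysis Set (FAS) and the FAS without the EAS, and adds: "All endpoints of the phase 1b will be descriptively analyzed".

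**The concern.** A best response is the most favourable status a subject reached, and later progression should not erase it. With PD ahead of SD, it does. A subject with stable disease at weeks 9 and 18 and PD at week 27 gets BOR = PD and does not count as disease control.

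Two consequences follow. First, the same label measures different things at different data cuts: a subject can be in DCR at the primary analysis and out of it at the 1-year repeat or the final analysis, only because a later PD was recorded. Second, iDCR does not lose iSD subjects this way, so the two disease control rates would differ partly because of the ranking and not because of the response criteria.

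**Working it through.** **Texts side by side.** Four places bear on the order.

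- The opening sentence of the same BOR definition lists SD before PD.
- The iBOR order puts iSD before iPD, and SAP Table 1 scores iPD, iSD, iPD as iSD.
- Protocol 10.5.3, in a phase 3 paragraph, treats disease control as stable disease or something better.
- Protocol Table 15 defines the target-lesion categories in the row order CR, PR, PD, SD, UE. It ranks nothing, but the match with the SAP order suggests where the slip came from.

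Protocol Table 16 gives visit-level responses only. No other passage overrides the written order.

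**Applying the rule.** SD before 56 days is entered as UE; BOR is then the highest-ranked included visit. In the table, SD means SD at 56 days or more after first dose unless noted.

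| Visit sequence | SAP order | SD moved above PD, nothing else | SD above PD, and SD after a first PD does not override it |
|---|---|---|---|
| SD, SD, PD | PD | SD | SD |
| PD, SD | PD | SD | PD |
| SD before 56 days, then PD | PD | PD | PD |
| SD, PR, PD | PR | PR | PR |
| PD, PR | PR | PR | PR |

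SD with no included PD visit (for example, SD then death, or PD first seen after non-study therapy) stays SD under every column.

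**All patterns.** There are 5 + 25 + 125 + 625 + 3125 = 3905 visit sequences of length 1 to 5 from CR, PR, SD, PD, UE. The first and last columns differ only in sequences over SD, PD, UE that contain both SD and PD, with SD first. For length n that is (3^n − 2·2^n + 1)/2, which gives 0 + 1 + 6 + 25 + 90 = 122. All 122 move from PD to SD, and no CR or PR result changes. A plain reorder changes 244; the extra 122 have PD before any SD. These count possible patterns, not subjects.

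**Who is exposed.** The first scan is at week 9 ± 1 week (Protocol 3.1.3.2), that is 56 to 70 days after first dose. Every SD at an in-window week-9 scan therefore passes the 56-day condition. On the 9-weekly schedule, the last subject enrolled has 1 scheduled scan at the primary analysis and up to 5 (weeks 9, 18, 27, 36, 45) by the 1-year repeat: up to 4 further chances for a week-9 SD to be rescored. Subjects enrolled earlier may already have had more scans at the primary analysis.

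**Effect per reclassified subject.**

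- EAS, about 27 expected (Protocol 10.2.1): 1/27 = 3.7 points.
- FAS, about 40: 1/40 = 2.5 points.
- FAS without the EAS, about 40 − 27 = 13: 1/13 = 7.7 points.

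**Illustration with assumed counts.** Take 27 subjects, 5 responders and 8 with SD at 56 days or more. With SD ranked above PD, DCR = 13/27 = 48.1%. Under the SAP order it is 9/27 = 33.3% if 4 of the 8 later have an included PD, and 5/27 = 18.5% if all 8 do.

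**The case against.** The strongest reply is that this is a drafting slip with little at stake. The SAP text contradicts itself, nothing shows that the printed order was programmed, and the endpoints are exploratory and descriptive. SAP Section 11 also records that the sponsor had already decided, after the phase 1b primary analysis, not to proceed to phase 3. No test or pending decision rests on this DCR. All of that stands and limits the consequence. It does not remove the error: the printed order is the operative derivation rule until it is corrected.

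A second objection is that a rule for SD after a first PD goes beyond the error and settles only half of the post-progression question, since a PR after PD still counts. The larger question does belong to the sponsor. But imaging continues until confirmed iPD (Protocol 3.1.3.2), so scans can follow a first RECIST PD, and a bare reorder would turn PD, SD into SD. The added sentence only keeps the result that sequence already has.

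Three smaller points also stand. DCR and iDCR would still differ by rule after the fix, because PD, SD stays PD while SAP Table 1 scores iPD, iSD, iPD as iSD. The figure of 13 assumes that the EAS lies within a FAS of 40, although the EAS is drawn from a safety set that requires only one of the two products. And the protocol asks investigators for RECIST v1.1 visit responses in phase 3 only, so the source of the phase 1b visit responses, and hence the number of subjects affected, is not known from the documents.

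**Conclusion.** The concern holds. As written, the RECIST v1.1 order gives the wrong best response to any phase 1b subject with SD at 56 days or more after first dose, no CR or PR, and a later included PD, and takes that subject out of DCR.

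The reach is narrow: BOR and DCR per modified RECIST v1.1. DLT, the irRECIST endpoints, the iORR used for the phase 3 decision, and RECIST ORR, CRR and DOR are unaffected. The size per subject is as computed above and rests on the planned set sizes. The total depends on how many stable subjects later had an included PD, and on whether the printed order was the one programmed. It should be corrected because a stated rule gives a wrong result and the repair is cheap.

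**What to change.** 1. State the order in SAP Section 6 as CR, PR, SD, PD, UE.
2. Remove the reference to protocol Table 15 as the source of the order.
3. Add that an SD recorded after a first RECIST PD does not override that PD.
4. Check which order was programmed. If it was the printed one, regenerate BOR and DCR per modified RECIST v1.1 for each analysis already run.

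Separately, the sponsor should state whether a CR or PR after a first RECIST PD counts. That choice would change RECIST ORR, CRR and DOR and is not part of this correction.

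The cost is two sentences of SAP text and one derivation step, plus a rerun of the BOR and DCR tables if item 4 calls for it. Items 1 to 3 change no CR or PR classification.
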